Remotely-Delivered Benefits Counseling for Service
Connection Applicants

NCT02677428

4/9/19

Project Description

1. Principal Investigator

[name]

2. Project Title

Remotely-Delivered Benefits Counseling for Service Connection Applicants

3. Purpose

The purpose of this study is to evaluate the utility of Remotely-Delivered Benefits Counseling in a 24-week clinical trial. This study will evaluate the effectiveness of Benefits Counseling on work and work-related outcomes with Veterans who are applying for service-connection. This study has the following specific aims and hypotheses:

Primary Aim 1: To estimate the effect of Remotely-Delivered Benefits Counseling on the slopes of paid work over time.

Hypothesis: The slopes of hours of paid work over time will differ between the control and Benefits Counseling groups, as evidenced by a significant, positive treatment-by-time interaction effect.

Exploratory Aim One: To estimate the effect of Remotely-Delivered Benefits Counseling on other outcomes.

Hypothesis: The slopes of hours of volunteer work; days attending school, days in vocational rehabilitation settings, days engaged in any one of the work-related activities; and income earned over time will differ between the control and Benefits Counseling groups.

Exploratory Aim Two: To conduct bivariate analyses of two of the components of mediation of Benefits Counseling's effects---correlation with the group assignment and with the outcome:

Hypothesis 2A: Assignment to Benefits Counseling (vs. control) will be associated with one or more of the following: (i) more positive changes in ratings of work's importance, (ii) greater decreases in beliefs that working and service connection are linked, and (iii) more positive changes in number of weeks attending any mental health or vocational counseling.

Hypothesis 2B: Individual slopes in hours worked over time will be associated with one or more of the potential mediators (i, ii, iii) as above in Hypothesis 2A.

4. Background

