- b. The VBA site with fact sheets about the different types of benefits available to Veterans. The topics covered in these fact sheets are: General Benefit Information, Veterans with Service-Connected Disabilities, Veterans with Limited Income, Education and Training for Veterans, Home Loans, Dependents and Survivors' Benefits, Burial and Memorial Benefits, and Insurance.
- c. The VBA websites for the local C&P office where issues pertaining to an individual Veteran's specific application are addressed. The site includes phone numbers to call with questions, e-mail contacts and directions to the VBA office.

3. Role of Therapists in Control Condition: The therapists in the control condition will differ from the Benefits Counseling therapist as shown in the table below

Control Therapist	Benefits Counseling Therapist
Initiate calls to Veterans at weeks 1 and 2	Initiate calls to Veteran at weeks 1 and 2 and around time of Module Three (or thereafter)
Up to three therapy calls of up to 30 minutes each	Up to three therapy calls of up to 30 minutes each
Convey information about Veterans Benefits	Convey information about Veterans Benefits AND vocational issues
Offer to elaborate on information on control websites	Inquiry about modules on Benefits Counseling website. Follow-up inquiries about domains covered on site.

Justification of Sample Size

We estimate that 190 Veterans will be enrolled and complete baseline assessments; 130 will log-in to the randomization site and be assigned to a treatment condition; 104 (52 per condition) will complete at least one follow-up assessment.

Precision Analysis

Consistent with the purpose of a pilot study, the sample size was selected to

estimate the standardized effect of treatment with reasonable precision, rather than to power for a statistically significant effect [50]; A **sample size of 52 per treatment condition** permits estimation of an expected standardized difference in slopes of hours worked between Benefits Counseling and control groups (e.g., (slopeBC-slopeCON)/SDslope) of $\delta=.40$ with a 95% confidence interval of (.01, .79). This effect would reflect an average 6% increase in baseline number of hours worked per month, or a total increase of 43% by month 6. Assuming an average baseline event rate of 40 hours/28 days and no change in the control group, this effect is equivalent to approximately 17 additional hours (approximately 2 days) of work per month by month 6.

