2. The SF-36 will be used to measure self-rated quality of life. The SF-36 was derived from the Medical Outcomes Study to assess health-related quality of life [51]. Patients answer 36 questions about health related impairments in daily activities, impairments from illness, and psychological states.

3. Alcohol, Smoking and Substance Involvement Screening Test (ASSIST): The ASSIST consists of eight questions concerning use of alcohol and or drugs, mostly within a three-month timeframe. It includes inquiries about amount of use, and incorporates questions that are somewhat indirect such as whether anyone else asked the Veteran to cut-down on use [60]. The ASSIST has excellent reliability [61] and validity [62].
4. The Disability Application Appraisal Inventory [28] was developed to better understand VA disability claimants' views of disability application and the role the beliefs play in clinical presentation. It is composed of 3 scales assessing (i) understanding of the claims process (Knowledge scale), (ii) expectations specific to the process (Negative Expectations scale), and (iii) the reasons becoming service connected is important to Veterans (Importance scale). The Disability Application Appraisal Inventory's test-retest reliability, internal consistency, factor structure and validation against selected MMPI subscales were tested and the measure has good reliability and construct validity [28].
5. The Post Traumatic Stress Disorder Checklist for DSM5 is a 20-item update [3] of the extensively validated earlier version [63], which had excellent agreement with comprehensive observer ratings [64, 65]. Veterans are asked to rate their agreement on a 5-point Likert scale with statements about how bothered the Veteran has been by each symptom in the past month, and the total score is the sum of the 20 item scores. The wording is general enough to rate PTSD symptoms related to Military Sexual Trauma as well as Combat Trauma and it has been sensitive to treatment effects in behavior therapy trials [66].

Outcomes Measured Repeatedly (Baseline, Weeks 4, 12, and 24)

1. Work and rehabilitative activities. A time-line-follow-back method will be used to determine whether and on what days the Veteran engaged in different work-related activities.

--- work for pay (in-kind compensation such as reduced rent is only counted when it is a formal arrangement)

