1. Determination of Study Outcomes: We list below the outcome measures whose scoring requires explication. Many of the scales' scoring is embedded in our earlier description of the measure.

a. Primary Outcome: The a priori definition of a primary outcome reduces the risk of Type I error. The number of hours paid work will be the primary treatment outcome. As noted previously, this includes work that is formal or under-the-table, and includes formal in-kind arrangements. It does not include days engaged in informal in-kind arrangements (housekeeping) or illegal activities such as gambling.

b. Secondary Outcomes: Secondary outcomes include each of the other work-related activities considered separately (unpaid work, attending school, engaging in vocational rehabilitation). Another secondary outcome is days engaged in any of the above work-related activities. This measure of work-related activities has a range of 0 to 28 in that each day is scored for whether any work-related activity was engaged in on that day as a dichotomous (0,1) value.

Dollars earned will be log-transformed (adding “1” to totals before transformation to allow calculation for veterans with no income) for outcome analyses if it is heavily skewed by outliers with high incomes.

c. Scoring of Clinical Measures.

- i. Psychiatric Symptomatology: The Global Severity Index from the Brief Symptom Inventory will be the main outcome from the BSI. The depression subscale will be scored too because of the association between depression and poor work function.
- ii. The SF-36 will be scored to yield standardized Mental Health and Physical Health Component Scores, with a mean of 50 and population standard deviation of 10. As noted earlier, the PTSD Checklist items are summed to yield a single score.
- iii. For the Work-Related Attitudes Scale, EFA will be conducted if it can be accomplished with the sample, i.e., if there is approximately a 10:1 participant:item ratio and item communalities are high [.6 or greater] after dropping any items with poor variability. If EFA is not feasible, we will analyze inter-item correlations and estimate internal consistency reliabilities to identify items that cluster together within a domain that reflect the perceived work-benefits relationship. A mean score of all items in this domain (or domains, if more than one is identified), will be generated.
- iv. The ASSIST yields an overall substance use severity score.

d. Process Measures

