3. Evaluation of Treatment Effects: For baseline values potentially related to outcome, evaluation of comparability of the two treatment groups will be conducted using chi-square tests for categorical variables and t-tests for continuous variables. If an unexpected difference is found and is related to the outcome, the potentially significant confounding variable will be added to the primary outcome analysis as a covariate.

The principal strategy for assessing the efficacy of the study treatment will be random effects regression, which will be used to determine the differences in slopes of outcomes between Veterans assigned to Benefits Counseling compared to Control. The model will include covariates described in the Introduction Section, time measured in weeks, and the contrasts of Benefits Counseling versus Control. A linear effect of time on outcome variables is being hypothesized but ancillary analyses will be conducted to determine if the effect of Benefits Counseling treatment is better explained by a quadratic function (as described in the Introduction section of this grant). Models will be specified to accommodate the observed distributions of outcomes (e.g., Poisson, normal, Bernoulli) and theory, model estimates, and fit indices will inform the specification of effects as fixed or random, and the structure of the variance-covariance matrix.

Our principal data analyses will be conducted on all randomized Veterans. We will attempt to follow all participants who are randomized for assessments regardless of their retention in treatment. Intention-to-treat analyses will be supplemented by analyses to describe the consistency of findings across different definitions of the sample: e.g., module-completers and treatment completers. Measures of engagement in Benefits Counseling will also be tested for their association with outcomes (number of days using the website, modules completed, minutes on phone with Benefits Counselor).

4. Evaluation of Processes that Might Mediate Treatment Response: This study is not powered for full mediation analyses but will allow for bivariate analyses of the components of mediation. Bivariate analyses will be conducted of the relationship between the slope of each potential mediator and (1) group assignment and (2) slope of hours worked per week. The partial correlation of group assignment with the slope of hours worked per week will be calculated, controlling in turn for each potential mediator's slope.

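### The primary slope model is not committed to a common baseline mean, although baseline paid hours are measured before randomisation; fixing it would give a modest, uncertain gain in precision

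*Combined protocol and SAP*

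**What the plan says.** All references are to the combined protocol and SAP.

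- **Outcome and target.** Data Analysis, item 1a: "The number of hours paid work will be the primary treatment outcome". Purpose, Primary Aim 1: the slopes will differ "as evidenced by a significant, positive treatment-by-time interaction effect".
- **Model.** Data Analysis, item 3: "The principal strategy for assessing the efficacy of the study treatment will be random effects regression". Its terms are covariates that the text says are described in an Introduction section, "time measured in weeks, and the contrasts of Benefits Counseling versus Control". The effect of time is taken as linear, with a quadratic form as an ancillary analysis. Distribution and random effects stay open: "Models will be specified to accommodate the observed distributions of outcomes (e.g., Poisson, normal, Bernoulli".
- **Baseline values.** The same item compares the arms at baseline with chi-square and t-tests. "If an unexpected difference is found and is related to the outcome, the potentially significant confounding variable will be added" to the primary analysis as a covariate.
- **Timing.** Paid hours fall under "Outcomes Measured Repeatedly (Baseline, Weeks 4, 12, and 24". The Study Design Overview places the baseline evaluation before the log-on at which assignment is received.
- **Precision.** The Precision Analysis expects a standardised slope difference of .40 with 95% interval (.01, .79) at 52 per arm, described as "approximately 17 additional hours (approximately 2 days) of work per month by month 6".

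**The concern.** Assignment is received after baseline, so among randomised Veterans the two arms have the same expected paid hours at week 0. A model with group, time and group-by-time terms nevertheless gives each arm its own week-0 mean. Chance imbalance at baseline then passes into the estimated slopes: an arm that starts low by chance tends to show a steeper fitted rise.

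The one stated safeguard lets an observed difference decide whether the primary model changes. A constraint fixed in advance uses the same information without a data-driven step.

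What is at stake is precision. The trial is sized for the width of its interval, not for power, and the planned lower limit is .01.

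**Working it through.** **Inputs from the document:** visits at weeks 0, 4, 12 and 24; 52 per arm; effect .40; 95% interval (.01, .79). **Not in the document, so assumed:** residual variance s², intercept variance t0², slope variance t1² and intercept-slope covariance t01.

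1. **The plan's figure.** SE = √(2/52) = .196. With the t quantile on 102 df, 1.983 × .196 = .389, giving (.011, .789), which rounds to the stated interval. It is a plain two-sample comparison of slopes with no allowance for a common baseline. Power at .40 is 53%.

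2. **Formula.** Let a and b be one Veteran's fitted intercept and slope. The mean visit week is 10, and the sum of squares about it is 0 + 16 + 144 + 576 − 4 × 100 = 336. Then
   - Var(b) = t1² + s²/336
   - Var(a) = t0² + s²(1/4 + 100/336) = t0² + .5476 s²
   - Cov(a, b) = t01 − 10 s²/336

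   With complete visits, fixing the week-0 arm difference at zero multiplies the variance of the slope contrast by R = 1 − Cov(a, b)² / [Var(a) Var(b)]. R cannot exceed 1. It equals 1 when t01 = 10 s²/336, a positive covariance that cancels the other term.

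3. **Central case.** Take t0² = s² = 1, t1² = 1/336, t01 = 0. Var(b) = 2/336, Var(a) = 1.5476, Cov = −10/336. R = 1 − (100/336)/(2 × 1.5476) = 1 − .2976/3.0952 = .904. The SE ratio is √.904 = .951, the half-width .389 × .951 = .370, and the interval about (.03, .77). This is worth 52/.904 ≈ 58 per arm; power at .40 goes from 53% to 57%.

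4. **Range.** The grid has 39 settings: intercept share of level variance .3 to .7, true-slope share of slope variance 0 to .75, intercept-slope correlation −.3 to +.5.

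| Correlation | R |
|---|---|
| −.3 | .67 to .84 |
| 0 | .70 to .97 |
| +.3 | .86 to 1.00 |
| +.5 | .90 to 1.00 |

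   The median R is .92, and in 26 of the 39 settings the variance falls by no more than 15%.

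5. **Second grid, in hours.** Residual SD 15-30 h, intercept SD 20-30 h, fitted-slope SD 17/.40 = 42.5 h over 24 weeks. R is .66-.86 at correlation −.3, .74-.99 at 0 (median .92) and .82-1.00 at +.3 (median .98).

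6. **Dropout.** With 65 randomised per arm, 13 of them with baseline only, and some later dropout (assumed), the central R is .92.

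7. **Simulation.** REML fits, 150 runs per setting, some with convergence warnings. In the central case under no effect, the mean SE was .195 unconstrained and .185 constrained, with 6.0% rejection for both. At correlation +.3 the SEs were .195 and .193, with rejection 10.0% and 10.7%. So few runs show only that the two fits behave alike; they do not settle the error rate.

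8. **Non-linear effects.** The constrained slope is b − [Cov(a, b)/Var(a)] a, applied to arm differences. In the central case Cov/Var(a) = −(10/336)/1.5476 = −.01923.
   - Full effect from week 4 (differences 0, 1, 1, 1): b = 10/336 and a = .75 − 10 × 10/336 = .452. Slope × 24 is .71 unconstrained and 24 × (.02976 + .01923 × .452) = .92 constrained.
   - Effect at week 24 only (0, 0, 0, 1): b = 14/336 and a = .25 − 10 × 14/336 = −.167. The values are 1.00 and 24 × (.04167 − .01923 × .167) = .92.
   - Over the grid in hours at zero correlation, the constrained values run .79-1.04 and .88-.97.

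**The case against.** **The text is silent, not wrong.** Item 3 mentions neither a week-0 group effect nor its absence, and the contrast it names could be the slope contrast alone. The covariates are referred to a section that cannot be found in the document, so baseline hours could be among them. This stands: the plan leaves the matter open, and the conventional reading is an inference.

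**Baseline is not ignored.** A reader might infer that the trial fails to adjust for baseline. The document does not support that. Baseline hours are the first repeated outcome, so each slope already starts from the Veteran's own baseline. The choice is between two valid parameterisations.

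**The gain may be negligible.** The Precision Analysis is multiplicative: exp(6 × .06) = 1.433 and 40 × .433 = 17.3 h. Dividing 17 h by .40 therefore moves a log-scale effect onto an hours scale, and 42.5 h is not a figure the plan implies. Proportional growth also makes change in hours correlate positively with baseline: about +.14 to +.28 in a check that assumed log-normal baseline hours, the eligibility cap of 24 h per week, and independent log slopes with SD .15 per month. At +.3 the median gain in the hours grid is only 2%. This stands. Neither a log link nor the cap was modelled in the variance calculations.

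**It is not free of consequences.** A reader might infer that the constraint has no downside. It also makes the fitted effect start from zero and run linearly, and step 8 shows that the estimate moves if the effect does not. The plan foresees this possibility: it has a quadratic check, it justifies the visits by early and by later-emerging effects, and Module Three follows the claim decision. This stands as a small cost. Neither fit is right for every non-linear pattern.

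**No gain from Veterans without a baseline.** A reader might expect such Veterans to contribute. Baseline is required before randomisation, so there should be hardly any.

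**Conclusion.** The point holds as a modest improvement, not as an error of validity. The plan does not commit to equal week-0 means although its design guarantees them. On the conventional reading it spends information on a difference known to be zero and leaves baseline imbalance to a significance test.

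Under a linear model, with assumed variance components, the constraint typically cuts the variance of the slope contrast by about 0-15% and at most by about a third. The cut is close to nil when Veterans with more baseline hours also rise faster. It cannot increase the variance. Reductions of a quarter to a third belong to settings with noisy hours or a negative intercept-slope correlation, and should not be promised.

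The validity of the constraint rests on randomisation after baseline and on analysing all randomised Veterans, which the plan intends.

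**What to change.** In Data Analysis, item 3, state before the data are examined by arm that:

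- baseline paid hours are the week-0 response in the primary model;
- the model has time and group-by-time terms and the prespecified covariates, with no group main effect at week 0 (equal baseline means), on whatever link is chosen;
- group-by-time remains the primary contrast;
- the rule that tests for imbalance and then adds a covariate does not apply to baseline hours;
- the unconstrained fit is reported as a sensitivity analysis beside the planned quadratic check.

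If the investigators prefer to keep a week-0 group term, the plan should say so and give the reason. The cost is a few lines of SAP text and one extra model fit. It needs no more Veterans, visits or data.

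### Hypothesis 2B tests the mediator-to-hours association without group in the model, so it partly restates Hypothesis 2A and the primary aim

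*Combined protocol and SAP*

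**What the plan says.** Section 3 (Purpose) sets Exploratory Aim Two as follows: "To conduct bivariate analyses of two of the components of mediation of Benefits Counseling's effects---correlation with the group assignment and with the outcome". Hypothesis 2A covers the first component: "Assignment to Benefits Counseling (vs. control) will be associated with one or more of the following", followed by three candidates (work importance, beliefs linking work to service connection, and weeks in counseling). Hypothesis 2B covers the second: "Individual slopes in hours worked over time will be associated with one or more of the potential mediators".

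Data Analysis section 4 puts this into practice: "Bivariate analyses will be conducted of the relationship between the slope of each potential mediator and (1) group assignment and (2) slope of hours worked". Its next sentence plans one adjusted quantity: "The partial correlation of group assignment with the slope of hours worked per week will be calculated, controlling in turn for each potential". What is held fixed there is the slope of the mediator, not group. The section also states its own limit: "This study is not powered for full mediation analyses but will allow for bivariate analyses of the components of mediation".

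No significance level is given for Hypothesis 2B and no effect size for any mediator. The plan does not say how a participant's slope is to be obtained.

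**The concern.** In a mediation argument, the second component is the association between mediator and outcome with treatment held fixed. The plan tests that association without holding treatment fixed. If counseling changes an attitude and, by a separate route, changes hours, the two arms differ in mean on both variables. That difference alone produces a correlation across the combined sample.

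The plan expects both shifts. Hypothesis 2A predicts an effect on the mediators, and Primary Aim 1 predicts an effect on hours, "as evidenced by a significant, positive treatment-by-time interaction effect". In the scenario the trial hopes for, a variable unrelated to work within either arm can therefore satisfy Hypothesis 2B, and the tendency grows with the treatment's success. What is at stake is which attitudes or service-use changes the report points to as possible carriers of the effect. The problem does not depend on the time order of the measurements and would remain with perfect ordering.

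**Working it through.** **Inputs from the documents.** 104 participants with follow-up, 52 per arm (Justification of Sample Size). Planning effect on the hours slope: .40 SD, with 95% CI (.01, .79) (Precision Analysis). Effect in the earlier face-to-face trial: .69 (Evidence of Benefits Counseling's Efficacy).

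**Assumptions.** Mediator effect dM from 0 to 1.0 SD, counted in the hypothesised direction; two-sided 5% test; normal slopes; unadjusted analysis over both arms; true within-arm correlation zero.

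**The plan's own figure.** .40 ± 1.96 × √(2/52 + .40²/(4 × 52)) = .40 ± 1.96 × .198 = (.012, .788), which rounds to the stated (.01, .79). The plan gives no figure for Hypothesis 2B.

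**Induced correlation.** Write G for group, M for mediator slope and H for hours slope. With equal arms, an effect d in within-arm SD units gives r = d/√(d² + 4) with group. With no within-arm link, r(M,H) = r(G,M) × r(G,H).

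- .40/.40: .40/√4.16 = .196, and .196² = .038.
- .69/.69: .69/√4.4761 = .326, and .326² = .106.

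**Rejection rate.** By Fisher's z with N = 104, the test statistic is centred at √101 × atanh(r).

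- r = .0385: centre .387. P(Z > 1.573) + P(Z < −2.347) = .058 + .009 = 6.7%.
- r = .1064: centre 1.073. P(Z > .887) + P(Z < −3.033) = .188 + .001 = 18.9%.

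Simulated rates follow, from 60,000 data sets per setting except the .40/.5 row, which used 4,000. A repeat simulation of six of these settings agreed to within half a percentage point.

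| Hours effect | Mediator effect (assumed) | Induced r | Unadjusted rejection |
|---|---|---|---|
| .40 | 0 | 0 | 5.0% |
| .40 | .2 | .020 | 5.5% |
| .40 | .4 | .038 | 6.7% |
| .40 | .5 | .048 | 7.8% |
| .40 | .69 | .064 | 9.7% |
| .40 | 1.0 | .088 | 14.4% |
| .69 | .4 | .064 | 9.8% |
| .69 | .69 | .106 | 19.1% |
| .69 | 1.0 | .146 | 32.5% |

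The smallest significant correlation at N = 104 is about .19. With all 130 randomised participants, the rates are 7.0% at .40/.40 and 22.6% at .69/.69.

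**With group in the model.** r(M,H|G) = [r(M,H) − r(G,M) r(G,H)] / √[(1 − r(G,M)²)(1 − r(G,H)²)]. The numerator is zero when there is no within-arm link. In the 60,000-run settings its rejection rate was 4.8% to 5.3%, at N = 104 and N = 130.

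**Passing both hypotheses.** At N = 104, the chance that one such variable is significant under both 2A and 2B is 4.1% at .40/.40 and 18.6% at .69/.69.

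**The opposite error.** With a true within-arm correlation of −.25 and both effects at .69, the unadjusted test rejects 21% of the time and the adjusted test 73%. Omitting group can hide a link as well as create one.

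**The case against.** Four points can be made for the plan.

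1. **It claims little.** The aim is exploratory, limited to bivariate components and declared unpowered for full mediation. Hypothesis 2B says only that the variables will be associated, and in the scenarios above a marginal association does exist. This stands in part. A rejection is false only as evidence for the mediation component, but the aim presents the correlation as such a component. Lack of power excuses imprecision; it does not excuse leaving out group.

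2. **The planned partial correlation is an informal check.** For a variable with no within-arm link, the group-hours correlation hardly moves after control for the mediator: .196 to .190 at .40/.5, .196 to .176 at .40/1.0, and .326 to .295 at .69/1.0. An attentive reader would see that such a variable explains little of the effect. r(M,H|G) also follows algebraically from the three pairwise correlations. This stands as a partial safeguard, but the plan does not say that r(M,H|G) will be calculated, tested or reported.

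3. **The large rates need large effects.** They require assumed mediator effects of about .7 to 1.0 SD, or the face-to-face trial's .69. At .40/.40 the induced r of .038 is under 0.2% of variance (.038² = .0014). This stands.

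4. **Use of both arms without adjustment is inferred.** If individual slopes are deviations from a model that already contains treatment-by-time, the group difference has been removed and the artefact largely disappears. This stands as a possibility. The documents neither state nor exclude it.

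**Conclusion.** The point holds as a limited correction to an exploratory analysis. On its natural reading, the plan never tests the mediator-to-hours association given group, and what it tests instead partly repeats Hypothesis 2A and the primary aim. At the planning effect the inflation is small: about 5% to 8% for assumed mediator effects of .2 to .5. It is material only with larger effects: about 14% at .40/1.0, 19% at .69/.69 and 32% at .69/1.0. These figures rest on assumed mediator effects, an assumed 5% level, normal slopes and unadjusted use of both arms.

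A reader might infer that Hypothesis 2B is bound to mislead, or that the trial will declare false mediators about a third of the time. The documents do not support that. They give no mediator effect, no significance level for 2B and no rule that turns a significant 2B result into a finding of mediation. They plan around .40, not .69. Nor does the point reach the primary comparison, the sample size or the handling of participants.

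**What to change.** In Data Analysis section 4, item (2), and in Hypothesis 2B, specify that the association between each mediator slope and the hours slope is tested with group in the model. This can be the partial correlation controlling for group, or a regression of the hours slope on mediator slope and group. Report it beside the planned group-hours partial correlation.

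State also how individual slopes are estimated, and in particular whether they are deviations from a model that already contains treatment-by-time. The cost is one model term and a sentence or two of text, with no new data and no change to trial conduct.
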